## 3.7 Clinical trials of Pfs48/45-based vaccines

Only one Pfs48/45-based vaccine has reached clinical trials. R0.6C is a multistage chimera consisting of a transmission blocking (Pfs48/45-6C) and a blood-stage (GLURP-R0) antigen. In preclinical studies using the *Lactoccus lactis* expression system, the GLURP-R0 antigen facilitated synthesis of a correctly folded Pfs48/45 C-terminal fragment [70]. Then, a series of novel fusion proteins were generated and tested in rats with aluminium hydroxide as an adjuvant [73]. Functional transmission-blocking antibodies were generated with transmission-blocking activity associated with specific IgG levels [73].

The safety and efficacy of this R0.6C vaccine is currently being tested in the Netherlands in healthy adults as a Phase I clinical trial. The STOP-TRANS study [NCT04862416] commenced recruitment in May 2021 and aims to recruit 32 participants across four groups. The single domain R0.6C vaccine will be adjuvanted with Alhydrogel alone, or combined with Matrix-M.

Of note is the fact that R0.6C consists of just a single domain of Pfs48/45 whereas the vaccine we are studying in this proposed trial contains all three domains of the protein. Transmission blocking epitopes have been found within all three domains of Pfs48/45, hence a full length Pfs48/45 vaccine offers more targets to elicit transmission blocking antibodies against, compared to R0.6C. [65, 76-79].

## **4 PFS48/45 IN MATRIX-M VACCINE DEVELOPMENT**

### 4.1 Characteristics of Pfs48/45 in Matrix-M

Pfs48/45 is a soluble protein vaccine based on the *P. falciparum* transmission-blocking target antigen. The Pfs48/45 protein is based on the sequence from the 3D7 *P. falciparum* strain. The recombinant protein is expressed in, and secreted from, the insect Schneider 2 (S2) cell line derived from *Melanogaster drosophila*.

Matrix-M is a potent, saponin-based adjuvant, comprising defined purified fractions from bark extracts of the bark of the *Quillaja saponaria* Molina tree, phosphatidylcholine and cholesterol, formulated as a 40nm-sized complex. Matrix-M adjuvant has been shown to efficiently activate and recruit immune cells to the draining lymph node, including T-cells, B-cells, NK-cells, dendritic cells and granulocytes, which may lead to enhanced antigen presentation [80]. Matrix-M has demonstrated a favourable safety profile, as well as the enhancement of cellular and humoral immune responses to a range of vaccine [80-82].

Pfs48/45 and Matrix-M adjuvant will be mixed immediately prior to administration for co-administration.

## 4.2 Vaccine development strategy

The clinical development of Pfs48/45 in Matrix-M adjuvant is aimed towards the production of an effective transmission-blocking malaria vaccine for individuals in malaria endemic regions. This vaccine would be used in a three-dose vaccination regimen (Table 1).

[figure not shown]
Group	Group size	D0	D28	D56
Group 1	8-10	Pfs48/45 10 μg Matrix-M 50 μg	Pfs48/45 10 μg Matrix-M 50 μg	Pfs48/45 10 μg Matrix-M 50 μg
Group 2	8-10	Pfs48/45 50 μg Matrix-M 50 μg	Pfs48/45 50 μg Matrix-M 50 μg	Pfs48/45 50 μg Matrix-M 50 μg
Group 3	8-10	Pfs48/45 50 μg Matrix-M 50 μg	Pfs48/45 50 μg Matrix-M 50 μg	Pfs48/45 10 μg Matrix-M 50 μg

Table 1: Vaccination protocol for study groups 1, 2 and 3

This first-in-human, dose-escalation study aims to provide an initial assessment of the frequency and magnitude of AEs following vaccination with Pfs48/45 in the Matrix-M adjuvant for evaluation of safety, as well as immunogenicity and *ex vivo* efficacy via membrane feeding assays. In addition, the optimal dose of Pfs48/45 in Matrix-M1 will be determined from this trial. Data generated from this study will inform progression to a Phase Ib trial in an endemic region to evaluate the safety and immunogenicity of Pfs48/45 in Matrix-M at various doses, in a similar dose-escalation study, to establish the optimal dose and schedule in an endemic setting.

[figure not shown]
## 4.3 Pfs48/45 immunogenicity and ex vivo efficacy in pre-clinical studies

The Pfs48/45 soluble protein vaccine being studied in this proposed trial is the full-length protein consisting of all three protein domains. In pre-clinical studies involving mice, the immunogenicity of different proteins (as measured by anti-Pfs48/45 IgG titres) was assessed by ELISA. Here, three 5 µg doses of different forms of the protein was administered to each group three weeks apart with AddaVax as an adjuvant. Figure 4 shows that mice immunised with both versions of the full-length protein had high levels of anti-Pfs48/45 IgG titres.

[figure not shown]
**Figure 4:** Anti-Pfs48/45 IgG titres in mice immunised with different forms of the Pfs48/45 protein. CD1 outbred mice were immunised with three 5  $\mu$ g doses of vaccine three weeks apart with AddaVax as an adjuvant and IgG titres measured at two weeks following the third dose. The following protein were assessed: Full-length Pfs48/45 protein (AA: 27-428) with all seven N-glycans sites (Pfs48/45 + N-Gly), full-length Pfs48/45 protein with all seven N-glycans sites mutated out (Pfs48/45 – N-Gly Mutant). OVA=ovalbumin (negative control).

In addition, SMFA showed that full-length Pfs48/45 induces transmission reducing activity (TRA) when IgG antibodies from immunised mice was diluted into blood containing stage V NF54 gametocytes and fed to 3-6 day old starved female *Anopheles stephensi* mosquitoes (Figure 5). Here, there were decreased oocyst numbers per mosquito when mice were immunised with full-length Pfs48/45 compared with controls.

**Figure 5:** Standard membrane feeding assay (SMFA) involving mice immunized with different forms of the Pfs48/45 protein at a concentration of 750  $\mu$ g/ml of purified IgG. Red numbers above each column denote percentage transmission reducing activity (%TRA) for each protein. OVA = ovalbumin (negative control); 4B7 = Pfs25 specific mouse control monoclonal antibody (positive control); Pfs48/45 + N-Gly = full-length Pfs48/45 with all seven N-glycans sites present; s48/45-FL – N-Gly Mutant = full-length Pfs48/45 with all seven N-glycans sites absent.

Finally, data suggests that the combination of Pfs48/45 with Matrix-M resulted in higher immunogenicity in mice when compared to Pfs48/45 with Alhydrogel (Figure 6). Here, CD1 outbred mice were immunised with two doses of 0.1  $\mu$ g or 1  $\mu$ g Pfs48/45 three weeks apart with Alhydrogel or Matrix-M. They were bled at three weeks following the second dose and immunogenicity assessed by anti-Pfs48/45 IgG ELISA and SMFA. The ELISA data suggests that the Matrix-M adjuvant potentiated increased levels of anti-Pfs48/45 IgG titres when compared to the Alhydrogel adjuvant, with minimal difference between the 0.1  $\mu$ g and 1  $\mu$ g dose.

**Figure 6:** Comparison of Alhydrogel and Matrix-M as adjuvants for immunisation with Pfs48/45. CD1 outbred mice were immunized with either two doses of 0.1  $\mu$ g or 1  $\mu$ g of Pfs48/45 with either adjuvant at three-week intervals and bled at day 20 and day 42. A: Pfs48/45 specific IgG endpoint titres of immunized mice. B: SMFA of IgG purified from D42 of immunized mice. Normal mouse sera acts as a negative control and the Pfs25 specific mAb 4B7 as positive control.

## 4.4 Clinical experience with Pfs48/45 in Matrix-M

There is no prior clinical experience with the Pfs48/45 protein specifically in the Matrix-M adjuvant.

Matrix-M adjuvant, has been administered to tens of thousands of individuals in clinical trials across the USA, Europe, Africa and Australia. In addition to trials involving vaccines to respiratory syncytial virus, influenza and SARS-CoV-2, two malaria pre-erythrocytic candidate vaccines (ChAd63/MVA ME-TRAP and VLP R21) have been administered with Matrix-M adjuvant in four phase I and phase I/II trials conducted in Oxford and Burkina Faso (ClinicalTrials.gov identifiers: NCT02572388, NCT02925403, NCT01669512, NCT02905019). A phase III trial involving 4800 children has recently started in Africa with sites in Burkina Faso, Mali, Kenya and Tanzania. Available safety data demonstrates that the Matrix-M adjuvant is well-tolerated with acceptable short-term reactogenicity and unremarkable long-term safety profile in COVID-19 vaccine clinical trials conducted by Novavax collaborators in subjects who received Matrix-M [83].

The profile of AEs following vaccination with Pfs48/45 may be partially predicted from previous studies assessing protein vaccines using the Matrix-M adjuvant. Local AEs are likely to include injection site pain, erythema, swelling, itching and warmth. Forseeable systemic AEs would include headache, fatigue, myalgia, arthralgia, malaise, feverishness, fever and nausea.

#### **5 INVESTIGATIONAL PRODUCTS**

## 5.1 Pfs48/45

## 5.1.1 Vaccine supply

Pfs48/45 is manufactured by GenIbet (Oeiras, Portugal), where the vaccines are formulated and vialed. Xerimis Ltd (Reading, UK) will perform certification and QP release, labelling and storage of the Pfs48/45 for investigational use only, and later supply to the clinical site (CCVTM).

## 5.1.2 Vaccine formulation and packaging

The Pfs48/45 protein drug product is formulated in 20 mM Tris Buffered Saline (TBS), 150mM NaCl, pH 7.4 (adjusted by sodium hydroxide). The final 0.2  $\mu$ m filtered drug product was dispensed manually using an electronic dispenser preset to deliver 500  $\mu$ l into type 1, 2 ml glass vials. Filling is performed by Apotex Production and Laboratory. The vials were sterilized and depyrogenated with a 13 mm grey bromobutyl rubber stopper supplied by Adelphi Healthcare Packaging (Haywards Heath, UK) and a 13 mm complete tear off, clear lacquered aluminium seal. The containers and closures were tested for compliance with defined specifications.

### 5.1.3 Storage of Vaccines

All vaccines will be stored at -80°C (nominal). All movements of the study vaccines will be documented. Vaccine accountability, storage, shipment and handling will be in accordance with relevant local Standard Operating Procedures (SOPs) and forms.

#### 5.2 Matrix-M

#### 5.2.1 Matrix-M adjuvant supply

Matrix-M adjuvant will be supplied to Xerimis by Novavax AB (Uppsala, Sweden), a subsidiary of Novavax, Inc (Gaithersburg, USA), where the adjuvant is formulated and vialed. Matrix-M will be labelled for investigational use only by Xermis Ltd before supplying the adjuvant to the clinical site.

All adjuvants will be certified for release by a qualified person (QP) at Xerimis Ltd.

## 5.2.2 Matrix-M adjuvant formulation and packaging

Matrix-M is formulated at a concentration of 0.375mg/ml in PBS. The drug product is filled into sterile 3 mL glass vials. Matrix-M adjuvant is a slightly brown to colourless, slightly opalescent, non-viscous liquid.

## 5.2.3 Matrix-M adjuvant storage and Handling

Matrix-M adjuvant is stored refrigerated at 2 to 8°C. All movements of the adjuvant will be documented. Accountability, storage, shipment and handling of Matrix-M adjuvant will be in accordance with relevant local SOPs and forms.

## 5.3 Administration of Pfs48/45 in Matrix-M adjuvant

A mixture of Pfs48/45 at a dose of 10  $\mu$ g or 50  $\mu$ g, with 50  $\mu$ g of Matrix-M adjuvant will be administered to all volunteers. Matrix-M and Pfs48/45 will be mixed immediately prior to administration and will be administered intramuscularly within one hour of thawing of Pfs48/45.

All vaccines will be administered intramuscularly in the deltoid muscle of the non-dominant arm preferentially, according to SOP VC002 Vaccination. The vaccinating investigator will wear gloves

and eye protection. During administration of the vaccines, Advanced Life Support (ALS) drugs and resuscitation equipment will be immediately available for the management of anaphylaxis. On vaccination day, vaccines will be allowed to thaw to room temperature and administered within one hour. After insertion of the needle but before injection, aspiration should be attempted to ensure that the injection is not intravascular. A single vial of vaccine will be used per dose administered and any remaining vaccine not used will be discarded.

#### **6 OBJECTIVES AND ENDPOINTS**

## **6.1 Primary Objectives**

To assess safety and tolerability of the Pfs48/45 with Matrix-M vaccine at various doses in healthy adult volunteers.

#### 6.1.1 Primary Outcome Measures

The specific endpoints for safety and reactogenicity will be actively and passively collected data on AEs. The following parameters will be assessed:

- Occurrence of solicited local reactogenicity signs and symptoms for 7 days following each vaccination
- Occurrence of solicited systemic reactogenicity signs and symptoms for 7 days following each vaccination
- Occurrence of unsolicited adverse events (AEs) for 28 days following the vaccination
- Change from baseline for safety laboratory measures for 28 days following vaccination
- Occurrence of serious adverse events (SAEs) during the whole study duration
- Occurrence of AEs of special interest during the whole study duration

Solicited and unsolicited AE data will be collected at each clinic visit. It will be collected from ediaries, clinical review, clinical examination (including observations) and laboratory results. This AE data will be tabulated, detailing frequency, duration and severity of AEs.

Haematological and biochemical laboratory values will be presented according to local grading scales. SAEs, AEs of special interest and withdrawal due to AE(s)/SAE(s) will be described in detail. Volunteers will be followed for approximately 8 months following initial dose of Pfs48/45 with Matrix-M and approximately 6 months following the third dose.

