On days 140 and 240, volunteers will be assessed for serious adverse events, by interim history and physical examination, as deemed necessary by the Investigator. Blood tests will be performed as indicated in the schedule of attendances for these timepoints (Table 2). Blood will also be taken for exploratory immunology analysis. At any post-vaccination visit, where valid written, informed consent is in place, photographs may be taken for clinical comparison. Confidentiality will be maintained as described in Section 13.5.

	S	V1				V2				V3						
Attendance number	1	2	3	4	5	6	7	8	9	10	11	12	13	14	15	16
Timeline (days)		0	1	7	14	28	29	35	42	56	57	63	70	84	140	240
Window (days)	-90		±1	±2	-2/+4	-7/+14	±1	±2	-2/+4	-7/+14	±1	±2	-2/+4	-7/+14	±14	±14
Inclusion/Exclusion criteria	Х	Х														
Informed consent	Х	Х														
Physical observations*	Х	Х	Х	Х	Х	Х	Х	Х	Х	х	Х	Х	Х	х	Х	Х
Medical history/ examination	Х	(X)	(X)	(X)	(X)	(X)	(X)	(X)	(X)	(X)	(X)	(X)	(X)	(X)	(X)	(X)
Photographs		(X)	(X)	(X)	(X)	(X)	(X)	(X)	(X)	(X)	(X)	(X)	(X)	(X)	(X)	(X)
Urinalysis	Х															
Urine β-hCG**	Х	Х				х				х				Х		
Review contraindications		Х				х				х						
Review AEs & medications			Х	Х	х	х	Х	х	х	х	Х	Х	х	Х	х	х
Vaccination		Х				Х				х						
Diary card issued		Х				х				х						
Diary card collected						х				х				Х		
Immunology plasma (mL)		40	10	10	30	30	10	60	30	30	10	60	110	80	30	30
Immunology serum (mL)		40			20	40			40	40			30	40	20	20
RNA preservation (mL)		3	3			3	3			3	3					
Haematology (mL)#	2	2		2	2	2		2	2	2		2	2	2		
Biochemistry (mL) ##	3	3		3	3	3		3	3	3		3	3	3		
HLA typing (mL)		4														
HIV, HBV, HCV serology (mL)	5															
Total Blood Volume (mL)	10	92	13	15	55	78	13	65	75	78	13	65	145	125	50	50
Cumulative blood volume (mL)	10	102	115	130	185	263	276	341	416	494	507	572	717	842	892	942 \$

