### 10.3 Reporting Procedures for all AEs

All AEs occurring in the 28 days following each vaccination observed by the Investigator or reported by the volunteer, whether or not attributed to the study vaccine, will be recorded. Recording and reporting of all AEs will take place as detailed in SOP VC027. We will not record bruising due to blood-taking or cannulation. All AEs that result in a volunteer's withdrawal from the study will be followed up until a satisfactory resolution occurs, or until a non-study related causality is assigned (if the volunteer consents to this). SAEs will be collected throughout the entire trial period. For each participant, this means the safety reporting window per participant (from provision of study consent to final follow-up visit).

Each AE will be graded by the participant according to the table for grading severity of AEs (see Table 4). Severity gradings may be reviewed and discussed with the participants at the clinic visits. Volunteers will be instructed on how to self-assess the severity of these AEs. There will also be space on the e-diary to self-document unsolicited AEs, and whether medication was taken to relieve the symptoms.

The severity of clinical AEs will be assessed by the Investigators according to the scales in Tables 4-6. Severity grading for laboratory AEs are dependent on the Oxford University Hospitals laboratory's reference and will be graded according to the scales in the site-specific table that can be found in the Trial Master File (TMF). These ranges will be based on FDA guidance relative to local laboratory reference ranges [https://www.fda.gov/media/73679/download].

Grade	Severity			
GRADE 0	None			
GRADE 1	Mild: Transient or mild discomfort (< 48 hours); no medical intervention/therapy required			
GRADE 2	Moderate: Mild to moderate limitation in activity – some assistance may be needed; no or minimal medical intervention/therapy required			
GRADE 3	Severe: Marked limitation in activity, some assistance usually required; may require medical intervention/therapy			

Table 4: Severity grading criteria for AEs.

Physical Observations	Grade 1	Grade 2	Grade 3
Tachycardia – beats per min*	101-115	116-130	>130
Hypotension (systolic) mm Hg	85-89	80-84	<80
Hypertension (systolic) mm Hg**	141-159	160-179	≥180
Hypertension (diastolic) mm Hg**	91-99	100-109	≥110
Fever °C	37.6 – 38.0	38.1-39.0	>39.0

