### 10.7 Procedures to be followed in the event of abnormal findings

Eligibility for enrolment in the trial in terms of laboratory findings will be assessed as detailed in SOP VC027. Abnormal clinical findings from medical history, examination or blood tests will be assessed as to their clinical significance throughout the trial. Laboratory AEs will be assessed using the site-specific tables in the TMF. If a test is deemed clinically significant, it may be repeated, to ensure it is not a single occurrence. If a test remains clinically significant, the volunteer will be informed and appropriate medical care arranged as appropriate and with the permission of the volunteer. Decisions to exclude the volunteer from enrolling in the trial or to withdraw a volunteer from the trial will be at the discretion of the Investigator.

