#### 16 APPENDICES

Appendix A: laboratory values for exclusion

Laboratory parameters for inclusion/exclusion in the trial will be considered on an individual basis, with Investigator discretion for interpretation of results and the need for repeated or further tests. In general, volunteers will be excluded if a result at screening constitutes what would qualify as a grade 1 (or higher) laboratory adverse event, according to the laboratory adverse event tables (filed in the TMF), on repeat of an abnormal test result. Urinalysis at screening will be assessed as per the table below:

URINE ANALYSIS (using MULTISTIX)				
Protein* 2+ or Protein creatinine ratio of ≥ 50 mg/mmol				
Blood £	2+ on two dipstick tests			
Glucose	1+			

Table 8: Urinalysis assessment.

\*In the event of the dipstick testing positive for protein with ≥1+ protein urine should be sent for a protein creatinine ratio.

<sup>£ In the event of urine dipstick testing positive for ≥1+ blood with, or without, protein, a repeat dipstick test will be carried out to confirm haematuria. In volunteers of child-bearing potential, a menstrual history will be taken to elicit whether the participant is currently menstruating and if they are, urine dipstick will be repeated after 1 - 2 weeks. If blood and/or proteinuria persist in any volunteer, an interpretation of the results will be undertaken by the Investigator on an individual basis to determine if they will be excluded from the trial, and the appropriate follow-up arranged.

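### The primary laboratory outcome is change from baseline, but the only stated presentation is by grade, so the size of any change is lost and baseline is left undefined

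*Combined protocol and SAP*

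**What the plan says.** Section 6.1.1 introduces its list of primary outcome measures with "The following parameters will be assessed". One item is "Change from baseline for safety laboratory measures for 28 days following vaccination". The same section then says how data will be shown. For adverse events, whose sources include laboratory results: "This AE data will be tabulated, detailing frequency, duration and severity of AEs". For laboratory values: "Haematological and biochemical laboratory values will be presented according to local grading scales".

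On the grades, section 10.3 says "These ranges will be based on FDA guidance relative to local laboratory reference ranges", and section 10.7 says "Laboratory AEs will be assessed using the site-specific tables in the TMF". The table itself is held in the trial master file and is not part of the document.

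On the state of volunteers at entry, Appendix A says that in general "volunteers will be excluded if a result at screening constitutes what would qualify as a grade 1 (or higher) laboratory adverse event", on repeat of an abnormal result and with investigator discretion.

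Table 2 schedules haematology and biochemistry at screening, at D0 and at nine later visits: D7, 14, 28, 35, 42, 56, 63, 70 and 84. Section 11 consists of a sample-size paragraph. It expects the frequency and magnitude of the outcome measures to be estimated and compared, but gives no method for laboratory change.

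**The concern.** The outcome and its presentation do not match. Change from baseline is a within-person quantity. A grade is a category set by a population reference range, and it moves only when a value crosses a limit. Because volunteers in general start at Grade 0, a grade table after vaccination shows who crossed a limit. It does not show how far anyone moved, or whether a whole group moved within the range.

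Baseline is also open. It could be screening (up to 90 days before enrolment under section 9.3.1), D0, or the pre-dose sample for each vaccination. D28 and D56 are each a follow-up visit for one dose and the pre-dose visit for the next (sections 9.3.4 and 9.3.6). These choices can give different answers from the same data, and nothing fixes the choice before the data are seen.

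At stake is the dose comparison. Section 11.1 intends to judge the optimal dose partly on safety and tolerability, in groups of 8–10. In groups that small, counts of graded abnormalities say little about a systematic shift.

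**Working it through.** The plan states no figure for this outcome (no SD, effect size, alpha or power), so there is none to reproduce. The check has four parts.

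**1. Is a change summary given anywhere?** The places that deal with laboratory data are:
- Section 6.1.1: outcome is change from baseline; presentation is by grade.
- Section 10.3: grades relative to reference ranges.
- Section 10.7: clinical significance and site-specific grading tables.
- Sections 10.9.1 and 10.9.2: holding and stopping rules use Grade 3.
- Section 11.1: no analysis method.
- Appendix A: screening grade used for exclusion.

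None defines baseline, names a statistic for change, or provides a shift table. Section 9.3.2 lists the D0 venepuncture ahead of vaccination, so a pre-dose D0 sample will exist.

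**2. How much would a grade table miss?** This is an illustration on assumed inputs, since the documents give no analyte SD:
- analyte standardised to population SD 1;
- reference range ±1.96 SD, with grading starting at the limit;
- all baselines in range (Appendix A);
- within-person change normal with SD s = 0.4, 0.6 or 0.8;
- a uniform shift of 0.5 or 1.0 SD.

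The share still in range comes from simulating 400,000 volunteers per case. The power of a two-sided 5% one-sample t-test on change comes from the noncentral t with noncentrality (shift/s)·√n.

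| Shift | s | In range, no shift | In range, shifted | Power, n=8 | Power, n=10 |
|---|---|---|---|---|---|
| 0.5 | 0.4 | 96.8% | 93.2% | 0.86 | 0.94 |
| 0.5 | 0.6 | 93.9% | 90.5% | 0.53 | 0.65 |
| 0.5 | 0.8 | 90.2% | 87.1% | 0.33 | 0.42 |
| 1.0 | 0.4 | 96.8% | 83.0% | 1.00 | 1.00 |
| 1.0 | 0.6 | 94.0% | 80.9% | 0.98 | 1.00 |
| 1.0 | 0.8 | 90.3% | 78.1% | 0.86 | 0.94 |

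For shift 0.5, s = 0.6 and n = 10, the expected number out of range rises from 10 × (1 − 0.939) = 0.6 to 10 × (1 − 0.905) = 0.95. That is about a third of one volunteer. The change summary detects the same shift with power 0.65.

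**3. Precision of each summary taken alone.** The 95% half-width for a mean change, in units of the SD of change, is t(0.975, n−1)/√n:
- n=8: 2.365/2.828 = 0.84
- n=10: 2.262/3.162 = 0.72

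The Clopper–Pearson upper limit when no event is seen is 1 − 0.025^(1/n): 36.9% for 0/8 and 30.8% for 0/10. These two sets of figures are on different scales and answer different questions, so they should not be ranked against each other. The comparison that bears on the point is in part 2.

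**4. Blood volume for the haemoglobin change.** The Table 2 visit volumes add to the stated 842 mL at D84 and 942 mL at D240. The D84 figure includes 10 mL at screening and 125 mL at D84 itself. Neither can affect the change between the D0 and D84 samples as blood lost between them. The relevant volume is 842 − 10 − 125 = 707 mL, which counts the D0 draw (92 mL) and everything through D70.

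**The case against.** The best defence is that section 6.1.1 does not say laboratory values will be shown only by grade. It lists change from baseline among parameters to be assessed, section 11.1 speaks of magnitude, and nothing bars a numerical summary at reporting. That stands. A reader might infer that a primary outcome will go unreported, and the documents do not support it. What they support is that the stated presentation does not deliver the stated outcome and that no summary or baseline has been fixed.

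A second defence is that, with volunteers generally at Grade 0 on screening, a later grade is already a change from baseline. That also stands, in part: it is a coarse change. What is lost is the size of a change and movement within the range. The grading table cannot be seen, so some grades there may refer to the volunteer's own baseline. Even then the output would be categorical.

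Third, holding and stopping decisions use grades, so they would not change. That is correct, and it limits the severity.

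Fourth, a change summary brings its own problem. The five individually named biochemistry analytes in section 9.2.2, at nine visits in three groups, give 5 × 9 × 3 = 135 intervals, of which about 0.05 × 135 ≈ 7 would exclude zero by chance. A pooled summary raises this to 180 and about 9, before any blood-count or liver-function components. This is a reason to label the intervals, not to omit them.

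Finally, a reader might infer that haemoglobin change from D0 would isolate a vaccine effect. It would not. All groups share one bleed schedule and there is no unvaccinated control, so phlebotomy and vaccine effects stay mixed.

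**Conclusion.** The point holds as a mismatch between a primary outcome and its only stated presentation, together with an undefined baseline. It should be corrected before analysis. It does not threaten the safety oversight of individual volunteers, and the raw values will be collected in any case.

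On the illustrative assumptions, a uniform shift of 0.5 SD lowers the in-range share by only about 3 to 4 percentage points. A change-from-baseline summary would detect that shift with power 0.33–0.86 at n=8 and 0.42–0.94 at n=10. A shift of 1 SD lowers the in-range share by about 12 to 14 points and would be detected with power of at least 0.86. The size therefore depends on the within-person SD, which the documents do not give, and on normality and a uniform shift. The mismatch in the text depends on none of these.

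**What to change.** - Define baseline as the pre-dose D0 sample. State whether the D28 and D56 pre-dose values also serve as the reference for the 28 days after doses 2 and 3.
- Keep the grade table. For each analyte and each safety-blood visit from D7 to D84, add the change from baseline (mean or median with 95% CI) by group, and a table of grade shift from baseline.
- If a pooled summary is given, label it as combining three different regimens.
- Label all intervals as descriptive, without multiplicity control.
- Report haemoglobin change beside the volume drawn since the D0 sample (707 mL before the D84 sample). State that phlebotomy and vaccine effects cannot be separated without an unvaccinated control.

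No visit, sample or procedure changes. The cost is a set of extra tables and some intervals that will exclude zero by chance. Fixing the definitions before analysis also removes the chance to choose baseline and summary after seeing the data.
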